7.3. Center Pooling

The study will be conducted in a minimum of 4 investigational sites. Screening and surgical data will be summarized for overall subjects and for each site separately, to confirm homogeneity of subject's characteristics between sites.

PPDS Statistical Analysis Plan	
Version [Final v3.0] Page 12 of 18	Medtronic

Primary and secondary endpoint analysis will be run on overall subjects. In case of imbalance regarding subject's characteristics between sites, additional subgroup analyses for primary and secondary endpoints could be performed according to investigational sites.

7.4. Handling of Missing, Unused, and Spurious Data and Dropouts

No data imputation will be performed for missing data, excepted for (Quality of Life) Carolina Comfort Scale (CCS) Questionnaire analysis (see appendix A).

Subject's selection, practical monitoring all along the study will allow the most complete and accurate data collection.

For CCS questionnaires missing data, we apply the rules and programming code as described in the CCS User Guide (see Appendix B).

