10.12.3 Study Exit

A study exit eCRF is required for all subjects. Prior to exiting a subject from the study, it is recommended to follow the subject until all ongoing system and/or procedure related AEs are resolved or unresolved with no further actions planned. All data available through the time of the subject's exit will be used for analysis.

MDT17051PDS Version 4.0 Page 31 of 56

Subjects are urged to remain in the study as long as possible but may be exited from the study for any of the following situations:

- Study completed
- Subject lost to follow-up
- Subject death
- Subject did not meet inclusion/exclusion criteria
- Subject was not implanted with a (investigational) device
- Subject did not provide consent <or data use protection authorization>
- Subject chooses to withdraw (e.g., consent withdrawal, relocation to another geographic location)
- Investigator deems withdrawal necessary (e.g., medically justified, inclusion/exclusion criteria not met, failure of subject to maintain adequate study compliance)

If discontinuation is because of safety or lack of effectiveness, the subject may be asked to be followed for collecting safety data outside the clinical investigation.

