10.12.5 Lost to Follow-up (LTFU)

Subject (LTFU) should be avoided as much as possible, and investigators are urged to do their utmost best to maintain subject follow-up compliance.

Subjects are not considered lost to follow-up until the end of the study, before the database is locked.

As is the case before documenting a missed visit, the following should take place and be documented before considering them LTFU.

- Three (3) phone calls should be made to the subject. Each attempt should be clearly documented in the source documents and the response or lack thereof should be captured.
- If there is no response to the phone calls, then an official, certified letter should be written to the subject. A copy of the letter and return or delivery receipts should be retained in the

MDT17051PDS Version 4.0 Page 32 of 56

subject's source documentation.

• In case a subject can no longer be found, the monitor shall check the appropriateness of the site's attempts to contact the subject.

Prior to final database lock, when all due diligence attempts to contact have been made, the subject is considered lost to follow-up. The Sponsor must be notified and the Exit eCRF must be completed.

11. Risks and Benefits

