14.3 Statistical Analysis Endpoints

14.3.1 Primary Endpoint

Incidence of hernia recurrence within 12 months will be calculated on the FAS subjects who reach the 12-month follow-up including any subject with hernia recurrence diagnosed within the 12-month period following surgery (even if the subject has withdrawn from the study before the 12-month assessment).

The primary endpoint will be summarized using count, percentage, and the corresponding 95% confidence interval. Sub-group analyses on primary endpoints will be performed according to study needs and will be described in the Statistical Analysis Plan and the Clinical Study Report.

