Indication for ventral hernia surgery		х					

Study procedures and assessment are described in the study schematic below:

Page 8 of 18

		Version	[Final v3.0]		Page 9 o	f18		Medtronic
Procedure/Assessment (D	Screening Pay-30 to 0)	Operative (Day 0)	Discharge Assessment	1 Month (±14 days) Follow-up	3 Month (±14 days) Follow-up	12 m (±30 Follo	onths days) w-up	24 months (±30 days) Follow-up
	Can be con	nbined		(Visit)	(Visit)	(Vi	sit)	(Visit)
Type of access, defect closure and Surgical technique approach		х						
Mesh size, lot number, positioning and fixation		х						
Antibiotic prophylaxis		Х						
Area of mesh overlap		Х						
Surgeon satisfaction questionnaire		х						
Adverse events assessment		Х	Х	Х	Х	>	K	Х
Length of hospital stay			Х					
Hernia recurrence/reoperation				Х	Х	>	κ	Х
Study exit								X

6. Determination of Sample Size

Sample size has been determined based on an acceptable level of accuracy for the estimated rate of hernia recurrence at 12 months (primary endpoint).

Previous studies^{1,2} of the predicate device (Proceed[™] Surgical mesh) with similar study indications, population, and design (prospective study with a long-term follow-up with more than 100 subjects), have reported the incidence of recurrence at 12 months to range from 3.5% to 5.2%.

95% confidence intervals obtained from incidence rates between 3.5% and 5.2% with N=100 subjects are shown below. Precision of the recurrence rates range from \pm 3.6% to \pm 4.4% as the recurrence rate increases.

	Recurrence rate at 12-month (1 year)								
	3.5% 4.0% 4.5% 5.2%								
N	100	100	100	100					
95% CI	[0.0 % - 7.1 %]	[0.2% - 6.7%]	[0.4% - 8.6%]	[0.8% - 9.6%]					
accuracy (+/-)	3.6%	3.8%	4.1%	4.4%					

Anticipating an attrition rate of 20% at 12 months, 125 subjects will be enrolled for this study.

PPDS Statistical Analysis Plan	
Version [Final v3.0] Page 10 of 18	Medtronic

7. Statistical Methods

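### No planned analysis shows how far the 20% of subjects expected to lack a 12-month outcome could move the primary recurrence rate

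*SAP*

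**What the plan says.** SAP 7.9 defines the primary rate on the Full Analysis Set (FAS). The numerator is subjects with a recurrence diagnosed in the first 12 months. The denominator is those subjects plus recurrence-free subjects with at least 12 months of follow-up. Protocol 14.3.1 agrees in substance and makes clear that a recurrence found before withdrawal still counts. A subject who leaves recurrence-free before 12 months appears in neither part of the ratio.

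On missing data, SAP 7.4 states: "No data imputation will be performed for missing data, excepted for (Quality of Life) Carolina Comfort Scale (CCS) Questionnaire analysis". Protocol 14.6 has the same default but lets the SAP make exceptions, and the SAP makes none for recurrence.

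On the expected loss, SAP section 6 states: "Anticipating an attrition rate of 20% at 12 months, 125 subjects will be enrolled for this study". Precision is worked out for the remaining 100: "95% confidence intervals obtained from incidence rates between 3.5% and 5.2% with N=100 subjects are shown below". Protocol 14.3.1 sets the reporting: "The primary endpoint will be summarized using count, percentage, and the corresponding 95% confidence interval".

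Two other analyses use recurrence data. The Per Protocol Analysis Set (PPAS) repeats the primary analysis, but its members must also have the 12-month assessment (SAP 7.1.3). Kaplan-Meier time to recurrence is a secondary endpoint. Neither document plans a best-case or worst-case bound, a tipping point, or a comparison of subjects with and without a 12-month outcome.

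**The concern.** The share of subjects expected to have no 12-month outcome is about four to six times the event rate being estimated. When events are this rare, a few unseen recurrences among early leavers matter as much as the events that are seen. The planned half-widths of 3.6 to 4.4 points describe sampling error among subjects with known outcomes. They do not reflect uncertainty about the rest.

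The direction cannot be settled in advance. Keeping leavers who recurred while dropping leavers who did not pushes the rate up if leaving is unrelated to recurrence. Recurrences that go undetected in people who stop attending push it down.

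The planned analyses do not resolve this. The PPAS is restricted to subjects with the 12-month assessment, so it cannot test the effect of lacking one. Kaplan-Meier does use partial follow-up, but it assumes that censoring is uninformative, which is the assumption in doubt. A reader of the final report would have one rate and one interval, with no prespecified view of how far the missing outcomes could shift them.

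**Working it through.** **Inputs**
- 100 evaluable, 20% attrition, 125 enrolled: SAP section 6 and Protocol 14.5.
- Cited 12-month recurrence of 3.5% to 5.2% for the predicate device: same sections.
- Observed rate of 4.0%, taken as 4/100: an assumption, chosen because it is one of the plan's own planning columns.
- Ratio as defined in SAP 7.9.

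**1. Reproduce the plan's figures.** Enrolment: 100 / (1 − 0.20) = 125, as stated. Half-width: 1.96 × √(p(1 − p)/100) at p = 3.5%, 4.0%, 4.5% and 5.2% gives 3.60, 3.84, 4.06 and 4.35 points, matching the printed 3.6, 3.8, 4.1 and 4.4. (The upper limit printed for the 4.0% column is 6.7%, whereas 4.0 + 3.8 = 7.8. This does not affect the present point.)

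**2. Size of the gap.** Missing: 125 − 100 = 25. Relative to the expected event rate: 20/5.2 = 3.8 and 20/3.5 = 5.7, hence about four to six times.

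**3. FAS rate with k recurrences among the 25.** Rate = (4 + k)/125.

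| k | Risk among the 25 | Multiple of observed 4% | FAS rate |
|---|---|---|---|
| 0 | 0% | none recurred | 4/125 = 3.2% |
| 1 | 4% | 1x | 5/125 = 4.0% |
| 2 | 8% | 2x | 6/125 = 4.8% |
| 3 | 12% | 3x | 7/125 = 5.6% |
| 25 | 100% | all recurred | 29/125 = 23.2% |

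**4. Smallest k that passes 5.2%.** 5.2% × 125 = 6.5, so 7 events are needed. With 4 observed, that is 3 among the 25. With 3/100 observed it is 4, and with 5/100 it is 2.

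**5. How likely three or more is.** The binomial probability of at least 3 in 25 is 7.6% if the missing recur at 4%, 13.8% at 5.2%, and 59% at 12%. The answer depends almost entirely on a risk that the study will not observe.

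**6. Effect of one subject.** Adding one recurrence: 5/101 = 4.95%, a shift of 0.95 points. Adding one recurrence-free subject: 4/101 = 3.96%, a shift of 0.04 points. The cited range is 5.2 − 3.5 = 1.7 points wide.

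**The case against.** The strongest reply is that the study is descriptive. It has no hypothesis, margin or success criterion, and the cited range only served to plan precision, so crossing 5.2% changes no decision. The 2x and 3x scenarios (4.8%, 5.6%) also lie inside the sampling interval already planned around 4.0%, which is 0.2% to 7.8%. All of this stands. It limits what is at stake to interpretation. It does not make the sampling interval a measure of missing-data uncertainty.

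Second, the 25 are not blank. Recurrence is assessed at 1 and 3 months and at unscheduled visits, so someone who leaves after month 3 has documented recurrence-free time, and a full 12-month multiplier overstates what is unknown. This also stands, and the table should say so.

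Third, Protocol 10.6 allows remote visits and record review, Protocol 10.12.5 requires repeated contact attempts, and SAP 7.1.1 tabulates disposition and reasons for discontinuation. These may reduce or describe the missing data, but they do not bound its effect. A reader could work out the extreme bounds from the reported counts, but not the baseline comparison.

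Three stronger readings are tempting and not supported:
- *One subject could move the result by the whole cited range.* Step 6 shows at most about 0.95 points against 1.7.
- *The ratio conflicts with Protocol 10.12.3*, under which data up to a subject's "exit will be used for analysis". That section does not say that every datum enters the primary ratio, and the Kaplan-Meier analysis uses follow-up up to exit.
- *Silent subjects will be counted as recurrence-free*, because Protocol 10.12.5 says "Subjects are not considered lost to follow-up until the end of the study, before the database is locked". Protocol 14.3.1 limits the denominator to subjects who reach the 12-month follow-up, and Protocol 10.12.5 itself provides for documenting missed visits. What remains is that SAP 7.9 does not say how length of follow-up is measured.

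**Conclusion.** The point holds as a gap in the analysis plan, not as an error in the primary formula. The ratio is a reasonable headline, but nothing planned shows its sensitivity to the outcomes it omits. At the planned attrition and an observed 4/100, the logical bounds are 3.2% and 23.2%. The upper bound is extreme and not a realistic expectation. More plausible departures, with missing subjects at two or three times the observed risk, give 4.8% and 5.6%.

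The figures rest on three assumptions: attrition of exactly 20%, 4 recurrences among 100 known outcomes, and no credit for partial recurrence-free follow-up. Passing 5.2% matters only for how the result reads beside the predicate-device studies. It would not make the study fail. The change is worth making because the purpose is to confirm safety and performance and to support EU regulatory and post-market requirements, and the cited range is the only recurrence reference that the documents give.

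**What to change.** In SAP 7.4 and 7.9, keep the current formula as the main result and add the following before the 12-month analysis (SAP 7.8.2), so that the additions are prespecified:

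- (a) A sensitivity table on the full FAS (N = 125) with missing subjects at 1x, 2x and 3x the observed risk, plus the none-recurred and all-recurred bounds. A note should say that full-period multipliers are conservative for subjects with documented recurrence-free visits.
- (b) The number of recurrences among missing subjects that would take the rate above 5.2%, labelled as descriptive.
- (c) Baseline characteristics of subjects with and without a 12-month outcome.
- (d) A rule that follow-up ends at the last documented recurrence assessment, whether by clinic visit, remote contact or record review, and that a 12-month visit inside the ±30-day window counts as 12-month follow-up. Without the second part, a subject examined on schedule at month 11 could fall short of the SAP's 12-month requirement and leave the denominator.

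The cost is one SAP paragraph and two tables. No new data are needed, and Protocol 14.6 already lets the SAP depart from the no-imputation default. The downside is a little more analysis and wider reported uncertainty.

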7.5. Adjustments for Multiple Comparisons

Statistical analysis of primary and secondary endpoints is descriptive. No adjustment will be done.

7.6. Demographic and Other Baseline Characteristics

Screening and demographics characteristics, medical/surgical histories and risk-factors will be summarized using descriptive statistics.

7.7. Treatment Characteristics

For efficacy and safety endpoints assessment, some subgroup analyses may be run according to hernia characteristics, surgical technique and mesh characteristic (number of treated hernias, mesh size, number of implanted meshes...); all these characteristics may impact efficacy and safety results.

7.8. Interim Analyses

2 interim analyses will be run according to the following milestones:

7.8.1. First interim Analysis

Preliminary analysis will be conducted in the study when 30 enrolled subjects complete the 3 month follow-up time-point. The objective is to confirm safety of the product at 3 months. This 3-month time-point is consistent with the wound healing period and the Parietene™ DS Composite Mesh film degradation profile (completely degraded by bulk hydrolysis in less than 15 weeks). This interim analysis is driven by regulatory needs, to support CE marking submission.

Version [Final v3.0]

Through analysis of clinical data available on a predicate device (Proceed[™] surgical mesh) and similar Medtronic composite meshes (Parietene[™] Composite mesh, Parietex[™] Composite mesh) used in ventral hernia repair (primary and incisional) by open or laparoscopic approach assessed during short-term post-surgery report the following adverse event rates:

10.6% on the equivalent, Proceed[™] surgical mesh used in laparoscopic ventral hernia repair at 3-6 weeks followup²,

14.3% on Parietene[™] Composite mesh used in laparoscopic ventral hernia repair at 10 weeks follow-up (range 6-25 weeks)³,

To 25%, on Parietex[™] Composite mesh used in laparoscopic and open ventral hernia repair after 2 months followup with a population of 30 subjects⁴.

Based on these studies, adverse event rates were estimated to range between 11% and 25% and used to generate binomial probabilities to observe at least 1 or 2 AEs with a sample size of 30 subjects as shown in the table below.

N=30 subjects	Hypothetic procedure related adverse event rate					
prob. to observe:	11%	12%	14%	17%	20%	25%
≥ 1 AE	97.0%	97.8%	98.9%	99.6%	99.9%	100.0%
≥ 2 AEs	85.7%	89.0%	93.6%	97.3%	98.9%	99.8%

With an N=30 of enrolled and evaluable subjects at the time of interim analysis, and assuming an 11% adverse event rate, there is a 97% probability to observe at least 1 adverse event and an 85.7% probability to observe at least 2 adverse events. In addition, the probability to observe adverse events increases as the adverse event rate increases to a maximum of 100% and 99.8% for observation 1 and 2 adverse events respectively at an adverse event rate of 25%.

First interim analysis (Safety analysis at 3-months) will evaluate subject's disposition, screening data, demographics and occurrence of procedure or device-related AE occurring within 3-month from surgery, including:

PPDS Statistical Analysis Plan		
Version [Final v3.0] Page 14 of 1	3	Medtronic

➔ Incidence of procedure and/or device-related AE occurring within 3 month from-surgery overall, and according to:

- \circ Relation to the procedure
- \odot Relation to the device including anticipated and unanticipated ADEs,
- \circ Severity,
- \circ Seriousness

 $_{\odot}$ Time of AE occurrence (intra-operatively, between surgery and discharge, and within 1 and 3 months post-surgery)

- → Incidence of procedure and/or device-related AE occurring within 3 month from-surgery by SOC and PT
- → Incidence of procedure and/or device-related SAE occurring within 3 month from-surgery by SOC and PT
- → Listing of procedure and/or device-related AE
- → Listing or procedure and/or device-related SAE

7.8.2. Second Interim Analysis

A second interim analysis is planned to occur when all enrolled subjects complete the 12-month visit, to assess both primary and secondary endpoints, when possible.

7.9. Evaluation of Objectives

Study objectives will be assessed through study endpoints measurement.

The primary endpoint is incidence of hernia recurrence within 12 months following Parietene[™] DS Composite Mesh use in ventral hernia repair.

Incidence of hernia recurrence within 12 months will be measured on the FAS subjects and using the following calculation formula:

[Subjects with Recurrence diagnosed within the first 12month following surgery]

[Subjects with Recurrence diagnosed within the first 12month following surgery + Subjects free of recurrence with a follow-up ≥12months]

A confirmatory analysis of primary endpoint will be run using Per Protocol Analysis Set.

Secondary endpoints

- Incidence of adverse device effects (ADEs) intra-operatively, at discharge, within 1 month, 3 months, 12 months, and 24 months following Parietene[™] DS Composite mesh use in ventral hernia repair will be primarily assessed based on FAS, and secondarily using PPAS and SAS.
- Incidence of hernia recurrence at 1, 3 and 24 months. The evaluation of hernia recurrence will be performed during a physical examination, using the formula described previously, according to the different time-points, and based on FAS and PPAS.
- Time to hernia recurrence and time to adverse device effect occurrence (from surgery time-point), will be assessed using Kaplan Meyer estimates. FAS and PPAS will be used for time to hernia recurrence, while FAS, PPAS and SAS will be used for time to ADE occurrence analysis. Time to Device-related AEs occurrence may also be assessed using Kaplan Meyer estimates.
- Carolinas Comfort Scale[™] QOL questionnaires completed pre-operatively and at 1, 12 and 24 months postoperatively will be analyzed using the Carolina Comfort Scale User Guide recommendations and programming code (see Appendix B), and based on FAS and on PPAS.

Several Subgroup analyses will be performed. Comparative analyses will be performed by hernia type (primary hernia versus incisional hernia) on overall subjects and on a subgroup of subjects with robotically assisted laparoscopic repair. Results of subjects operated with robotically assisted laparoscopic repair will also be compared with subjects operated with a traditional Laparoscopic procedure.

Hernia recurrence will be assessed during physical examination at 1-month, 3-month, 12-month and 24-month assessment post-surgery. Remote follow-up visits due to COVID-19 related reasons may be performed: if hernia or hernia reoccurrence is suspected during a remote visit using questionnaires, the subject will be instructed to return to the clinic or hospital for diagnosis by the surgeon through clinical assessment. This process is fully accepted by scientific societies^{5,6,7,8,9}

7.10.Safety Evaluation

Safety will be assessed as the proportion of subjects with AE based on the FAS, PPAS and SAS; AE incidence will be reported overall, and according to:

- Relation to the procedure
- Relation to the device including anticipated and unanticipated ADEs,
- Severity,
- Seriousness.

PPDS Statistical Analysis Plan	
Version [Final v3.0] Page 16 of 18	Mectronic

Listing of AEs, SAEs, ADEs and SADEs, and UADEs will be provided based on FAS, PPAS and SAS, using the MEDRA coding system classification for AE terms, and including characteristics described previously and AE outcome.

7.11.Health Outcomes Analyses

Health outcomes analyses are already part of primary and secondary endpoints analyses, as described previously.

